8.5.4.2 Sensitivity Analyses for Triheptanoin-Naïve Cohort

8.5.4.2.1 Negative Binomial Regression in Triheptanoin-naïve

The comparison between pre- and post-UX007 MCE rates will also be performed using a negative binomial regression model, which accounts for different follow-up times, with the time that each subject stays in the study (study period 1) included as an offset in the model. This analytic model estimates the ratio of event rate of the post-UX007 treatment period over that of the pre-UX007 treatment period. The model can be performed using SAS GENMOD procedure where the REPEATED statement is used to account for the within patient comparison. Two-sided 95% confidence interval will be provided for the rate ratio along with the p-value.

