5.2 MCE

Major clinical events (MCE) include skeletal myopathy (rhabdomyolysis), hepatic (hypoglycemia) and cardiac disease (cardiomyopathy) events, and are defined as any visit to the ER/acute care, hospitalization, emergency intervention (i.e. any unscheduled administration of therapeutics at home or in the clinic), or any similar event whether caused primarily by LC-FAOD or by an intercurrent illness complicated by LC-FAOD.

5.3 Study Day 1

For all subjects, study day 1 is defined as the day of the first UX007 dose during Study UX007-CL202. For subjects who previously participated in study UX007-CL201, study day 1 coincides with the last UX007-CL201 visit.

Study Day 1 will be used to calculate the study days for all listings.

5.4 UX007 Treatment Day 1

UX007 treatment day 1 is defined as the day of the first UX007 dose. For subjects who rolled over from UX007-CL201, UX007 treatment day 1 is the day of the first UX007 dose during the UX007-CL201 study. For subjects who were UX007/trihep naïve, UX007 treatment day 1 coincides with study day 1.

UX007 treatment day 1 will be used to calculate days on UX007 for subjects who rolled over from UX007-CL201 and for naïve subjects in select statistical analyses.

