5.10.1 Study Period 1 (Main Study Period)

Study period 1, or the main study period, starts from study day 1 till the last visit day in CL202. The last visit date is the last date among the early termination visit date, the study completion visit date, the safety follow up visit date, or the last visit date as of a clinical cutoff date, if applicable. Study period 1 will be used for all efficacy on FAS and safety analyses unless otherwise specified.

5.10.2 Study Period 2

Study period 2 has the same ending date as Study period 1 but starts from UX007 treatment day 1. Study period 2 will be used in select analyses for UX007-CL201 rollover subjects.

[figure not shown]
5.10.3 Study Period 3

Study period 3 starts from the 18 months (548 days) preceding UX007 treatment day 1 and ends 1 day prior to UX007 treatment Day 1. Study Period 3 is referred as the retrospective period for MCE data collection.

Study period 3 will be used for UX007-CL201 rollover subjects and UX007/trihep naïve subjects only in select analyses.

The following figure illustrates the definitions of the three study periods.

Figure 5.10.3.1: Diagram of Study Periods in CL202

Study Period 1 is defined for all enrolled subjects in CL202; Study Period 2 is defined for CL201 rollover subjects only; Study Period 3 is defined for CL201 rollover subjects and UX007/trihep naïve subjects. CL201 treatment period exists for CL201 subjects only;

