5.11 Annualized Event Rate

The numbers of MCE will be annualized for each subject using the following formula:

$$\text{Annualized Event Rate} = \frac{\text{Number of events}}{\text{Duration of data collection period in days}/365.25}$$

The number of MCEs will be derived as the total number of events as recorded in the major clinical event CRF that occurred during the specific data collection period. Whenever an annualized rate is calculated over study period 1, the number of days is calculated from study day 1 till the data cutoff date or the early termination/study completion visit date for subjects who have early terminated/completed the study.

Annualized event rates will be calculated for MCEs overall and for each event type (ie., rhabdomyolysis, hypoglycemia, and cardiomyopathy respectively).

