8.5.4.1 Pre- and Post-UX007 Comparisons in MCE in Triheptanoin-Naïve Cohort

All MCE related endpoints (i.e., annualized event/duration rates of MCE overall and by event type) will be analyzed by comparing pre- and post-UX007 treatment period. The pre-UX007 treatment period for UX007/trihep naïve subjects corresponds to the retrospective MCE collection period, i.e., study period 3.

The 18 months pre-UX007 treatment period will be compared to the 18 months post-UX007 treatment period using the paired t-test. The Wilcoxon signed rank test will be performed as a nonparametric alternative to the paired t-test when the normality assumption is questionable. For subjects who had longer than 18 months of follow up on study as of the data cutoff date, MCEs that occurred between UX007 initiation and 18 months post UX007 initiation will be

included for calculating number of MCEs and total durations in days of MCEs will be calculated accordingly. For subjects who terminated the study prior to reaching 18 months on study, MCEs that occurred between UX007 initiation and the termination visit will be included for calculating number of MCEs and total durations in days of MCEs will be calculated accordingly. For historical annualized event rate and annualized duration rate observed during study period 3, the data collection period is 18 months (548 days) preceding the date of UX007 initiation. For subject's age less than 18 months at UX007 initiation, the data collection period will be between the birthdate and the date prior to UX007 initiation.

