8.5.5 CL201-Rollover Cohort: Integrated Analyses for efficacy endpoints

For UX007-CL201 rollover subjects, the long-term effects of UX007 will be assessed through both MCE related endpoints and non-MCE related efficacy parameters using data collected during study period 2, i.e., by integrating data collected from UX007-CL201 and UX007-CL202.

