8.5.5.2 Sensitivity Analyses for CL201-Rollover Cohort

8.5.5.2.1 Negative Binomial Regression in CL201-Rollover Cohort

The comparison between pre- and post-UX007 MCE rates will also be performed using a negative binomial regression model, which accounts for different follow-up times, with the time that each subject stays in the study included as an offset in the model. This analytic model estimates the ratio of event rate of the post-UX007 treatment period over that of the pre-UX007 treatment period. The model can be performed using SAS GENMOD procedure where the REPEATED statement is used to account for the within patient comparison. Two-sided 95% confidence interval will be provided for the rate ratio along with the p-value.

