11 APPENDICES

11.1 Summary of Efficacy Endpoints and Analysis

Table 11.1.1: Summary Table of UX007-CL202 Efficacy Endpoints and Analysis

Test / Instrument	Efficacy Endpoint	Analysis Population (Age criteria if applicable)	Type of Efficacy Analysis	Study Period (Visits selected if not all)	Statistical approach
MCE	Annualized event rate of MCE	Full analysis set	Primary	Period 1	Descriptive statistics
MCE	Annualized event rate of MCE by event type	Full analysis set	Secondary	Period 1	Descriptive statistics
	Annualized duration of MCE, and by event type	Full analysis set	Secondary	Period 1	Descriptive statistics
MCE	Annualized event rate of MCE and by event type; Annualized event rate of MCE and by event type;	UX007/trihep naïve subjects	Additional Efficacy Analyses	Period 1 & 3	Descriptive statistics & Comparison between pre- and post-UX007 MCE rates via paired t-test, Wilcoxon signed rank test, and NB
MCE	Annualized event rate of MCE and by event type; Annualized event rate of MCE and by event type;	UX007-CL201 rollover subjects	Integrated Analyses	Period 2 & 3	Descriptive statistics
ECHO	Change from baseline of EF, ventricle size, and SF	Full analysis set	Secondary	Period 1	Descriptive statistics
		UX007/trihep naïve subjects	Additional Efficacy Analyses	Period 1 (all visits)	Descriptive statistics & Paired t-test
		UX007-CL201 rollover subjects	Integrated Analyses	Period 2 (all visits)	Descriptive statistics

Test / Instrument	Efficacy Endpoint	Analysis Population (Age criteria if applicable)	Type of Efficacy Analysis	Study Period (Visits selected if not all)	Statistical approach
SF-12	Change from baseline –PCS, MCS, and individual domain	FAS-SF-12 (age ≥18)	Exploratory	Period 1 (all visits)	Descriptive statistics
		UX007/trihep naïve subjects in FAS-SF-12	Additional Efficacy Analysis	Period 1 (all visits)	Descriptive statistics & GEE
SF-10	Change from baseline –PHS and PSS	FAS (age ≥6 - <18)	Exploratory	Period 1	Descriptive statistics
		UX007/trihep naïve subjects in FAS-SF-10	Additional Efficacy Analysis	Period 1 (all visits)	Descriptive statistics & GEE
Clinical Biomarker	Change from baseline in serum creatine kinase, fasting serum glucose, ALT, AST, GGT	Full analysis set	Exploratory	Period 1 (all visits)	Descriptive statistics
		UX007/trihep naïve subjects	Additional Efficacy Analysis	Period 1 (all visits)	Descriptive statistics & Paired t-test

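### The naïve-cohort negative binomial model names only post-treatment time (study period 1) as its offset, so the pre-treatment count has no valid exposure

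*SAP*

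**What the plan says.** The naïve-cohort negative binomial model in SAP 8.5.4.2.1 estimates a post/pre event rate ratio within patients and is meant to allow for unequal follow-up. Its exposure is given as "with the time that each subject stays in the study (study period 1) included as an offset in the model". No other exposure appears in that section.

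The definitions fix what that period is:

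- SAP 5.10.1: "Study period 1, or the main study period, starts from study day 1 till the last visit day in CL202".
- SAP 5.4: "For subjects who were UX007/trihep naïve, UX007 treatment day 1 coincides with study day 1".
- SAP 8.5.4.1: the pre period is study period 3, for which "the data collection period is 18 months (548 days) preceding the date of UX007 initiation". For subjects under 18 months of age it runs from birth to the day before UX007.

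Two other places point to row-specific exposure. SAP 5.11 divides the number of events "that occurred during the specific data collection period" by the length of that same period. The naïve MCE row of Table 11.1.1 lists Periods 1 and 3 for the "Comparison between pre- and post-UX007 MCE rates via paired t-test, Wilcoxon signed rank test, and NB".

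For CL201 rollovers, SAP 8.5.5.2.1 repeats the offset wording without naming a period: "with the time that each subject stays in the study included as an offset in the model".

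**The concern.** A pre/post count model needs, on each row, the time over which that row's events were collected. The named offset is time after UX007 initiation and does not overlap the window that supplies the pre count. Read as written, the pre count is set against the wrong exposure.

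The section also does not say whether post events are counted over the first 18 months, as in 8.5.4.1, or over all of study period 1. The direction of the error depends on that choice, so the model could hide a benefit or create one. A gap between this model and the paired test that came only from the offset could be read as lack of robustness or as added benefit.

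**Working it through.** **Inputs from the documents.** Pre window T3 = 548 days (SAP 5.10.3 and 8.5.4.1; check: 18 × 30.4375 = 547.9). It is shorter in infants, and Protocol 7.3.1 admits subjects from 6 months of age. Study period 1, T1, is at most 2557 days (Month 84, Table 11.4.1). The SAP gives no event rate, ratio or sample size for this model, so there is no planned figure to reproduce.

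**Assumptions, not in the documents.** Pre rate 2 per year, gamma frailty with shape 1, true ratio 0.60 unless stated, and the follow-up, leaver and infant patterns shown.

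**Step 1: algebra.** With log(T1) on both rows, log E(pre) = a + log T1 and log E(post) = a + b + log T1. If T1 is the same for everyone, the offset cancels and exp(b) is a ratio of counts, not of rates: exp(b) = true ratio × (post days counted ÷ T3).

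**Step 2: all study period 1 events counted, uniform follow-up.**

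| Month | T1 (days) | T1/548 | True 0.60 reads |
|---|---|---|---|
| 12 | 365 | 0.666 | 0.40 |
| 18 | 548 | 1.000 | 0.60 |
| 36 | 1096 | 2.000 | 1.20 |
| 60 | 1826 | 3.332 | 2.00 |
| 84 | 2557 | 4.666 | 2.80 |

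Simulation (40,000 pairs per scenario, negative binomial GEE, log link, exchangeable correlation, to mirror GENMOD with REPEATED) gave 0.405, 1.213, 1.993 and 2.797 at 1, 3, 5 and 7 years.

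**Step 3: follow-up that varies.** Negative binomial weights depend on the fitted mean, and so on T1. The offset then no longer cancels exactly.

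| Follow-up spread evenly over | True 0.60 reads | True 1.0 reads | Step 1 formula at mean T1, true 0.60 |
|---|---|---|---|
| 0.5–3 y | 0.59 | 0.99 | 0.70 |
| 0.5–5 y | 0.87 | 1.45 | 1.10 |
| 1–7 y | 1.32 | 2.22 | 1.60 |

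In the first row the errors happen to offset each other. In a separate run with 40 subjects, 200 replicates, follow-up spread over 365–2557 days and no true effect, the shared offset gave a ratio of 2.19 and rejected in 99% of replicates. Row-specific offsets gave 0.99 and 4.5%.

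**Step 4: post events capped at 18 months, as in 8.5.4.1.** With full windows on both sides there is no error. Where windows differ, the Step 1 factor for one subject is 183/548 = 0.33 for a leaver at 6 months, and 548/183 = 2.99 for an infant with 183 pre days and a full post window. Across a cohort:

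| Pattern | Share 5% | 10% | 20% |
|---|---|---|---|
| Leave at 6 months; completers' study time 1.5 y | 0.56 | 0.53 | 0.46 |
| Same, completers' study time 3 y | 0.54 | 0.50 | 0.41 |
| True ratio 1.0; completers 1.5 y | 0.93 | 0.88 | 0.77 |
| True ratio 1.0; completers 3 y | 0.91 | 0.83 | 0.68 |
| Infants with a 9-month pre window, no leavers | 0.61 | 0.63 | 0.67 |

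Varying the pre rate (1, 2, 4 per year) and the shape (0.5, 1, 2) with 20% leavers gave 0.44 to 0.49 (completers 1.5 y) and 0.38 to 0.46 (3 y). Simulation spread is about 0.01.

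**Step 5: row-specific offsets.** In the 40,000-pair scenarios these gave 0.593 to 0.607 for a true 0.60 and 0.995 to 1.006 for a true 1.0.

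**Rollovers.** SAP 8.5.5 describes the cohort's long-term assessment as "using data collected during study period 2, i.e., by integrating data collected from UX007-CL201 and UX007-CL202", and Table 11.1.1 lists Periods 2 and 3. SAP 8.5.5.1 counts post events only to 18 months after UX007 initiation. The note to the table says it leaves out the MCE sensitivity analyses. The period meant in 8.5.5.2.1 is therefore open.

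**The case against.** The text does not say that study period 1 goes on both rows, and every figure above depends on that reading. The same section says the model allows for different follow-up times and estimates a ratio of rates, which a shared offset cannot do when windows differ. SAP 5.11, 8.5.4.1 and Table 11.1.1 supply the right exposures, so a careful programmer might well use them. This stands as a limit: the error is in the specification, and no wrong analysis has been shown. It does not remove the point. 8.5.4.1 gives the pre length only for annualized historical rates, and 8.5.4.2.1 names a different, defined period.

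The largest ratios need all study period 1 events to be counted. The section can also be read as following the 18-month comparison in 8.5.4.1, and the 7-year uniform case is a limit, not an expectation. That is fair.

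Under the cap, leavers and infants pull in opposite directions. With 5% or 10% of each (completers 1.5 y) the reading is 0.58 or 0.55, against 0.56 or 0.53 for leavers alone. The error shrinks but stays.

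Finally, this is a sensitivity analysis with no decision rule attached, and the primary analysis is descriptive. That bounds the consequence.

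**Conclusion.** The concern holds. For naïve subjects the only offset named is time after UX007 initiation, so it cannot be the exposure for the pre count. The rule as written conflicts with SAP 5.11 and Table 11.1.1.

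Under the shared-offset reading and the stated assumptions, the size runs from nothing (18-month cap with all windows full, or certain follow-up spreads) to a true 0.60 reported as 0.41 (cap, 20% leavers, completers 3 y) or as 2.80 (all events, uniform 7 years). The presence and direction of error depend on the post window, which the section leaves unstated, and on the follow-up distribution.

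The descriptive primary analysis and the paired t-test and Wilcoxon comparisons are unaffected. It should still be fixed, because unequal windows are what this model is meant to handle. For rollovers there is an ambiguity to settle, not a shown error.

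**What to change.** In SAP 8.5.4.2.1 and 8.5.5.2.1, replace the offset wording with text to this effect:

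- Each subject contributes one pre row and one post row. The offset is the natural log of the days in the data collection period over which that row's MCEs were counted.
- Pre row: 548 days, or the days from birth to the day before UX007 initiation if the subject is under 18 months old at initiation.
- Post row: the days from UX007 initiation to the end of the window over which post events are counted, ended at termination, completion or data cutoff.

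Then state the post window for each cohort: either 18 months, as in 8.5.4.1 and 8.5.5.1, or full follow-up (study period 1 for naïve subjects, study period 2 for rollovers). The choice is the sponsor's, and the row-specific offset is correct under either. Count and offset must end on the same day: study period 1 can run to the safety follow-up (5.10.1), where no MCE assessment is scheduled, whereas 5.11 stops at termination, completion or cutoff.

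Cost: wording in two sections and one derived variable. No new data are needed.

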8 STATISTICAL METHODS OF ANALYSES

8.1 General Principles

This statistical analyses are mostly descriptive analyses with statistical tests performed for select. All statistical tests will be two-sided and tested at statistical significant level of 0.05. The statistical analyses will be reported using summary tables, figures, and data listings. Continuous variables will be summarized by number of subjects and mean, standard deviation (SD), median, minimum, and maximum values. Categorical variables will be summarized by number and percentage of subjects. All raw data obtained from the CRFs will be included in data listings

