8.1.1 Repeated Measure Model: General Estimating Equations

When the sample size and number of observations are allowed, change from baseline endpoints over time will be analyzed using a generalized estimation equation (GEE) model that includes time as the categorical variable and adjusted for the baseline measurement. The covariance structure that will be used for the GEE model is compound symmetry which specifies constant variance for the assessments and constant covariance between the assessments over time. In general, the p-value will be presented for testing the statistical significance of the change from the baseline to assessments at Months 6, 12, 24, 60, 72, and 84, if applicable, respectively. For an analysis of change from baseline to assessment at a particular month, only measurements up to that month will be included in the model. For the analysis of change from baseline to assessments at Month 84, all measurements collected up to and including Month 84 will be included in the model.

If the number of observations are insufficient for analyses using a GEE model, a descriptive summary will be provided, and analyses using observations at a single time point, such as paired t-test or other nonparametric methodologies, may be considered.

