8.5.4.3 Analyses of Non-MCE Endpoints in Triheptanoin-naïve Cohort

When the sample size and number of observations are allowed, statistical tests will be performed on the following non-MCE endpoints to assess the statistical significance of change from the baseline to assessments at Months 6, 12, 24, 60, 72, and 84 if applicable, respectively. Two-sided 95% confidence interval and p-value will be presented at these visits.

- Echo variables: EF, ventricle size, and SF: the paired t-test will be used to assess the statistical significance of change from baseline variables. The Wilcoxon signed rank test will be performed if the normality assumption is questionable.
- Clinical biomarkers: the paired t-test will be used to assess the statistical significance of change from baseline variables. The Wilcoxon signed rank test will be performed if the normality assumption is questionable.
- SF-10 PHS and PSS: the GEE model as described in Section 8.1.1 will be used to analyze change from baseline scores.
- SF-12v2 PCS & MCS: the GEE model as described in Section 8.1.1 will be used to analyze change from baseline scores.

Statistical testing of the above endpoints will only be performed at the final analysis when the sample size permits. Summary statistics will be provided by visit at a snapshot analysis due to the anticipated limited number of subjects and number of observations at the time of a snapshot. Two-sided 95% confidence intervals will be presented for change from baseline values at all visits.

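### The negative binomial pre/post MCE rate ratios carry no small-sample correction or sample-size condition; run with default sandwich errors, their 95% CIs would be too narrow in a small cohort

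*SAP*

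**What the plan says.** SAP 8.5.4.2.1 adds a negative binomial comparison of pre- and post-UX007 MCE rates as a sensitivity analysis in the naïve cohort. On implementation it says that the model can be run in SAS GENMOD, where "the REPEATED statement is used to account for the within patient comparison". On output: "Two-sided 95% confidence interval will be provided for the rate ratio along with the p-value". SAP 8.5.5.2.1 repeats the model for rollover subjects: "The comparison between pre- and post-UX007 MCE rates will also be performed using a negative binomial regression model". SAP 8.1 sets the error rate: "All statistical tests will be two-sided and tested at statistical significant level of 0.05".

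Neither negative binomial section states the variance estimator, a finite-sample correction, the reference distribution or a minimum number of subjects.

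The surrounding analyses differ by cohort:
- **Naïve cohort.** SAP 8.5.4.1 makes a paired t-test the main MCE comparison, with the Wilcoxon signed rank test if normality is doubtful.
- **Rollover cohort.** SAP 8.5.5.1 announces a pre/post comparison but names no test, and Table 11.1.1 lists descriptive statistics only.
- **GEE for SF-10 and SF-12.** SAP 8.1.1 says "The covariance structure that will be used for the GEE model is compound symmetry", also without naming a standard error. Unlike the negative binomial models, it has a fallback: "If the number of observations are insufficient for analyses using a GEE model, a descriptive summary will be provided".

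**The concern.** A sandwich variance with a normal reference relies on many independent clusters. Here each subject is one cluster, contributing a pre count and a post count. With few subjects the sandwich estimate tends to be too small, and the normal critical value makes no allowance for its own sampling error. Skewed counts make both worse, because a few subjects with many events drive the estimate and its variance.

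The negative binomial rate ratio is the only pre/post MCE contrast for which the SAP promises an interval. In the naïve cohort it is meant to support a paired t-test that already uses n-1 degrees of freedom, so a liberal check could seem to confirm a result it does not really support. In the rollover cohort no other named test stands beside it.

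**Working it through.** **Inputs from the documents.** Two-sided 0.05 (SAP 8.1). Pre-treatment window of 18 months, 548 days, and a matching 18-month post window (SAP 8.5.4.1). Total enrolment about 100 (SAP 3.6) or about 150 (protocol 7.6.6), in three cohorts (SAP 5.6). Most subjects are expected to have prior exposure (SAP 3.1), which suggests that the naïve cohort is a minority. The plan gives no cohort size, event rate, dispersion or standard error, so it has no figure to reproduce. The test is whether the nominal 5% is attained.

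**Assumptions.** GENMOD with REPEATED reports sandwich standard errors with a normal reference unless told otherwise; this is a software default, not SAP text. Event rates and dispersions are assumed as stated below.

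**Estimator.** With one pre and one post count per subject over equal periods:
- log rate ratio = log(mean post / mean pre)
- sandwich variance = Σ(postᵢ/mean post − preᵢ/mean pre)² / n²

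On a simulated dataset of 15 subjects the closed form gave SE 0.5201. A negative binomial GEE fit gave the same value under independence and exchangeable working correlation, and with dispersion 0.5 or 1. In this layout the Mancl-DeRouen correction multiplies the SE by n/(n−1): 0.5201 × 15/14 = 0.5573, which the software also returned.

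**Type I error, equal 18-month windows.** 20,000 null runs per setting; 0.5 to 2 MCEs per year; between-subject dispersion 0.5 to 1; within-subject dispersion 0.25 to 1. Ranges are over four settings.

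| n | Default sandwich, normal | Mancl-DeRouen, t(n−1) |
|---|---|---|
| 15 | 10.3-14.2% | 6.2-9.3% |
| 20 | 9.2-12.5% | 6.0-8.8% |
| 30 | 7.6-10.2% | 5.8-7.9% |
| 40 | 7.1-9.7% | 5.7-8.0% |
| 70 | 6.3-7.8% | 5.5-7.0% |

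The cause shows in the standard errors. In the most dispersed setting at n=20, the mean estimated SE was 0.4096 against an empirical SD of 0.4949, a ratio of 0.83. At n=70 the ratio was 0.2458/0.2663 = 0.92.

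**Second set of assumptions.** At 1 to 2 MCEs per year and between-subject CV 1.0 to 1.4, the default rejected 9.5-17% at n=15, 9-15% at n=20, 8-12% at n=30 and 6-9% at n=60. With Mancl-DeRouen and t it rejected 5-12% at n=15 and 6-11% at n=20.

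**Unequal follow-up.** Post period varying from 0.5 to 5 years, each period with its own offset, 700 runs: 16.7% at n=10, 10.6% at n=20 and 7.1% at n=40. Corrected: 9.0%, 7.3% and 5.6%. At about 10%, the Monte Carlo error is √(0.1 × 0.9/700) = 1.1 percentage points.

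**Width after correction.** Relative width = [n/(n−1)] × t(0.975, n−1)/1.960.
- n=15: 1.0714 × 2.145/1.960 = 1.17
- n=20: 1.0526 × 2.093/1.960 = 1.12
- n=70: 1.0145 × 1.995/1.960 = 1.03

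**Alternatives under the null.** The paired t-test rejected 2.6-5.0%. A within-subject permutation test rejected about 2.5-5%. A subject-level percentile bootstrap CI failed to cover in 7.2-10.8% of runs at n=15, 6.9-9.3% at n=20 and 6.2-7.7% at n=30.

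**The case against.** The strongest reply is that little hangs on these models. The primary efficacy analysis is descriptive. In the naïve cohort the main MCE test is a paired t-test or Wilcoxon test, and the t-test kept its level in the simulations. This stands, and it limits the reach of the point.

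A reader might go further than the documents allow in three ways.
- **That the SAP expects small cohorts.** SAP 8.5.4.3 contains the words "due to the anticipated limited number of subjects and number of observations", but the sentence goes on to confine them to a snapshot analysis. It covers only the naïve cohort's non-MCE endpoints and explains why they are not tested at that time. It says nothing of MCE counts or the rollover cohort.
- **That the SAP prescribes uncorrected robust errors.** It is silent on the standard error and says only that the model can be run in GENMOD. The use of default errors is an inference.
- **That the GEE analyses are equally exposed.** They concern exploratory SF-10 and SF-12 scores, are conditional on sufficient data and have a fallback, though no threshold is given. In simulations with baseline centred at its true mean, the uncorrected GEE test rejected about 7% at n=20 and 6% at n=50.

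It is also fair to say that correction does not restore 5%; the table shows the remaining excess.

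**Conclusion.** The point holds for the two negative binomial models. Run literally with software defaults, they give intervals that are too narrow and p-values that are too small. The excess is serious at 15 to 20 subjects (about 9-17% instead of 5%), material at 30 (8-12%) and modest at 60 (6-9%). These figures rest on assumed event rates and dispersions, on the software default and on an unknown cohort size.

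The primary analysis and the naïve cohort's main test are unaffected. The consequence is greatest in the rollover cohort, where no other inferential MCE method is named. The GEE models are a secondary matter.

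**What to change.** In SAP 8.5.4.2.1 and 8.5.5.2.1:
- Specify a bias-corrected sandwich variance with a t reference for the rate ratio CI, for example Mancl-DeRouen, or MBN as offered in GLIMMIX. Mancl-DeRouen was simulated here; MBN was not.
- Take the p-value from a within-subject pre/post permutation test on the 18-month windows. Use annualized rates, or restrict the test to subjects with equal pre and post periods. Early termination and from-birth pre-periods make windows unequal. Swapping raw counts is then not valid and swapping annualized rates is only approximate, so the equal-period version is the cleaner one.
- State which window the CI and the p-value each refer to, because 8.5.4.2.1 takes its offset from study period 1.
- State that the corrected CI remains somewhat liberal with skewed counts. Do not use a percentile bootstrap as the main interval.

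The same variance correction may be applied to the GEE model in SAP 8.1.1.

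The cost is a possible change of SAS procedure, one added analysis per cohort, and CIs wider by about 12% at 20 subjects and 3% at 70. The permutation p-value and the CI may occasionally disagree, so the SAP should say which governs. No data collection changes.
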